| | 
28. Individuals in whom a skin-fold measurement of the cutaneous and subcutaneous tissue for eligible injection sites exceeds 40 mm.
 
29. History of severe allergic reactions (e.g., angioedema, anaphylaxis) or severe reactions to prior vaccination (e.g., severe injection site reaction, anaphylaxis).
 
30. Chronic or active neurologic disorder which, in the opinion of the investigator, would place the participant at risk of harm or injury. Note that individuals with stable headaches, stable peripheral neuropathy, and stable post-herpetic neuralgia may be included.
 
31. Confirmed syncopal episode determined or suspected to be of cardiac origin within 12 months of screening.
 
32. Significant or progressive ophthalmologic disease, including significant signs or symptoms of active disease.
 |
| TEST PRODUCT, DOSE, AND ROUTE OF ADMINISTRATION | 
 • HIV DNA vaccine (p24CE and p55gag) plasmids • IL-12 DNA plasmid • MVA/HIV62B (MVA62B) vaccine • TLR9 agonist (lefitolimod, MGN1703) • bNAb (VRC07-523LS and 10-1074) |
| DURATION OF SUBJECT PARTICIPATION AND DURATION OF STUDY | Subjects will be observed on study for up to 112 weeks. |
| CONCOMITANT MEDICATIONS | All subjects should be maintained on a stable antiretroviral drug regimen through the end of Stage 4 and then interrupt therapy. |
| PRIMARY ENDPOINTS | 
 • Proportion of individuals experiencing a grade 3 or greater adverse event, including signs/symptoms, lab toxicity, or clinical event, that is definitely, probably, or possibly related to the study treatment. • Proportion of treated individuals who achieve post-treatment control (PTC) of viral load, defined as having an undetectable viral load (<50 copies RNA/mL) at 24 weeks after initial rebound in viremia for those who rebound or through week 24 of the interruption for those who do not exhibit a rebound |
| SECONDARY ENDPOINTS | 
 • Number of unsolicited adverse events within 28 days after administration of each study agent. • Number of any severe adverse event, medically attended adverse event, or potentially immune-mediated medical |

| | |
|-----------------------------|---|

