3 STUDY OBJECTIVES

3.1 Primary Objectives

- To evaluate the safety and tolerability of combination regimen in which subjects will receive EP-administered IL-12 adjuvanted DNA vaccine (prime, Stages 1 and 2), heterologous MVA (boost, Stage 3), combination bNAbs/TLR9 adjuvant (Stage 4) and bNAbs during an ATI (ATI, Stage 5).
- To evaluate the impact of this 5-stage regimen on viral load set-point during a treatment interruption

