10.9 ART resumption phase (Stage 6)

Viral load criteria. Based on this rationale, we propose that treatment be initiated for any one of the following outcomes: (1) viremia > 50,000 copies RNA/mL for four weeks, (2) viremia > 10,000 copies RNA/mL for 6 weeks, (3) viremia > 2000 copies RNA/ml for 12 weeks or (4) viremia > 400 copies/RNA for 24 weeks. Operationally, this will allow for an acute viremic state that will need to resolve within 12 weeks, with high-level viremia only being allowed for a brief period. Post-treatment control (defined as viremia <400 copies RNA/mL) should be achieved prior to Week 24 post-virus rebound.

For any initial viral load greater than 400 copies/mL, we will bring individuals back immediately (within 3 working days or as soon as they are available) for a repeat test.

CD4+ T cell criteria. ART will also be reinitiated if the CD4+ T cell count declines to below 350 cells/μL on two consecutive visits. If an individual demonstrates a CD4+ T cell count <350 cells/uL, we will bring them back immediately (within 3 working days or as soon as they are available) for a repeat test.

Clinical criteria. ART will also be re-initiated for any symptoms suggestive of a severe acute retroviral syndrome, particularly signs of altered mental status or viral meningitis (severe headache, neck stiffness), but including unexplained rash, lymphadenopathy, and fevers. ART will also be re-initiated at the request of the study participant and/or her primary health care provider.

Post-ART monitoring. Once ART is reinitiated, subjects will be evaluated at Weeks 4 and 8 on ART. If viral load is not below the level of quantification by Week 8, participants will be evaluated every four weeks until the viral load is confirmed to less than the level of quantification. A follow up visit will occur 24 weeks after resumption of ART.

Routine safety studies, CD4+/CD8+ T cell counts and viral load will be performed at Weeks 4, 8, 24 and at any visits required between Week 8 and Week 24 to evaluate decrease of viral load to below level of quantification. Plasma and PBMCs will be collected and cryopreserved at the time of ART resumption and at Weeks 4, 8 and 24 on ART.

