15.4 Primary Efficacy Endpoint: Post-treatment Control

All subjects will undergo a treatment interruption designed to evaluate the primary outcome of “post-treatment control” (PTC), using the definition we recently used as part of the CHAMP Cohort collaboration¹³². In this study, PTCs were defined as individuals who remained off ART for ≥ 24 weeks and maintained viral loads ≤ 400 copies/mL for at least 2/3 of the time points. Viral loads > 400 HIV-1 RNA copies/mL were acceptable if the participant was subsequently able to suppress the viral load back to ≤ 400 HIV-1 RNA copies/mL and maintained virologic control for 24 weeks.

In our protocol, a combination of two bNAbs will be administered at the time ART is interrupted, and will likely have a persistent antiviral effect until levels wane to subtherapeutic levels, which we will assume to occur at about Week 12 of the ATI period. Also, we expect that in the post-ART and post-bNAb phase of the ATI that a period of acute viremia will occur, and that this could last for up several weeks. As described in Section 1.11, ART will be initiated if plasma HIV RNA levels remain consistently $> 50,000$ copies RNA/mL for four weeks, $> 10,000$ copies RNA/mL for six weeks, > 2000 copies RNA/mL for $>$

12 weeks, and > 400 copies RNA/mL > 24 weeks. In this scenario, post-treatment control will only be achieved once viremia falls below 400 copies RNA/mL and remains there for 24 weeks.

Success will hence be defined in two ways. First, subjects who fail to show any consistent rebound above 400 copies RNA/mL between Week 12 of the ATI (when bNAbs levels wane) and Week 36 of the ATI will be considered as having achieved post-treatment control. Second, subjects who exhibit a rebound and eventually achieve 24 weeks of virus control will be considered as having achieved post-treatment control.

Failure will be defined based on the need to resume ART due to high-level viremia, dropping CD4+ T cell counts, or clinical events (see Section 1.11).

The proportion of individuals who achieve our study-defined PTC will be the primary outcome.

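### The synopsis and Section 15.4 define the primary efficacy endpoint, post-treatment control, in incompatible ways, and nothing says which prevails

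*Combined protocol and SAP*

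**What the plan says.** The synopsis (Primary Endpoints) makes PTC the primary efficacy endpoint, "defined as having an undetectable viral load (<50 copies RNA/mL) at 24 weeks after initial rebound in viremia for those who rebound". Control must otherwise last "through week 24 of the interruption for those who do not exhibit a rebound". The sentence does not require the participant to be off ART at that reading, and no failure rule goes with it.

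Section 15.4 gives another rule. For those who rebound, "post-treatment control will only be achieved once viremia falls below 400 copies RNA/mL and remains there for 24 weeks". For the rest, success is the absence of "any consistent rebound above 400 copies RNA/mL between Week 12 of the ATI (when bNAbs levels wane) and Week 36 of the ATI". Failure is a need to restart ART because of high viremia, a falling CD4 count or a clinical event. The section also says that it uses a published cohort's definition, in which "PTCs were defined as individuals who remained off ART for ≥ 24 weeks" and had viral loads of 400 or less at two thirds or more of their time points.

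Section 5.1 names only plasma HIV RNA during the ATI. Section 15.6 sets the decision rule for the acute group: 6 or more PTC among 15, a null of 15%, and at least 80% power at a true rate of 47%. For the exploratory chronic group it uses 2 of 5 against 5%. Neither null is tied to a particular definition. Section 15.1 puts every eligible participant who starts therapy into the efficacy analysis.

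**The concern.** The two rules differ in threshold (50 or 400 copies/mL), in duration (one reading or 24 weeks), in the start of the clock (first rebound or return below 400) and in the window for non-rebounders. They therefore do not count the same people. The test compares a small count with a fixed historical rate, so it is interpretable only if the count and the rate rest on the same definition. The trial is open-label with one arm, and the documents state no order of precedence. The definition could therefore be settled after the viral loads are known.

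**Working it through.** **1. The plan's own figures.** Inputs from Section 15.6: n = 15, cut-off 6, null 0.15, alternative 0.47. The test, from the synopsis, is a likelihood ratio test.

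- Exact tail: P(X ≥ 6 | 15, p) = Σ C(15,x) p^x (1−p)^(15−x), summed over x = 6 to 15. At p = 0.15 this is 0.0168, and at p = 0.47 it is 0.788. The stated 80% is reached at about 47.6%, so the plan's figure is reproduced to within two percentage points.
- Likelihood ratio: G = 2[x ln(p̂/0.15) + (15−x) ln((1−p̂)/0.85)], referred to chi-square with 1 df. For x = 6, G = 2[6 ln(0.400/0.15) + 9 ln(0.600/0.85)] = 5.50, P = 0.019. For x = 5, G = 3.13, P = 0.077 (exact P = 0.062).

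The cut-off of 6 is right. The line between success and failure is one participant wide.

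**2. The two rules side by side.**

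| Feature | Synopsis | Section 15.4 |
|---|---|---|
| Threshold | <50 copies/mL | <400 copies/mL |
| Rebounders | one reading, 24 weeks after first rebound | below threshold for 24 weeks |
| Non-rebounders | through ATI week 24 | ATI weeks 12 to 36 |
| Off ART | not stated | in the cited cohort definition; restart for three named reasons is failure |

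**3. Participants who change status.**

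- Rebounds, then stays at 200 copies/mL off ART for 24 weeks: 200 is above 50, so failure under the synopsis; 200 is below 400 for 24 weeks, so success under Section 15.4.
- First rebound at ATI week 28, sustained above 400, then ART restarted for viremia: no rebound through week 24, so this can be success under the synopsis. The rebound lies inside weeks 12 to 36 and ART was resumed, so it is failure under Section 15.4.

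**4. Antibody-free observation for non-rebounders.** Section 15.4 assumes that antibody levels wane at about ATI week 12. The synopsis window then leaves 24 − 12 = 12 weeks, against 36 − 12 = 24 weeks in Section 15.4. The dosing table in Section 1.3 expects VRC07-523LS to persist at least 12 to 16 weeks. At 16 weeks, the synopsis window leaves 24 − 16 = 8.

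**5. Outcomes that Section 15.4 does not classify.** Its failure rule omits restarts at participant or provider request (Section 10.9), for pregnancy (Section 10.8), and for SARS-CoV-2 infection, shelter-in-place or COVID-19 vaccination (Appendix C). Appendix C also allows participants to opt out of the ATI, yet Section 15.1 keeps them in the analysis.

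Follow-up adds one more group. Study weeks 34 to 86 give 52 weeks of ATI, so 24 weeks of control must begin by ATI week 52 − 24 = 28. A participant who rebounds at about week 12 and regains control 24 weeks later, at week 36, would need follow-up to ATI week 36 + 24 = 60.

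**6. Sensitivity of the error rate (assumed inputs).** Suppose a share f of non-controllers is counted as success after re-suppression on ART. The effective null is then 0.15 + 0.85f. Type I error of the 6-of-15 rule is 0.0168 at f = 0, 0.052 at f = 5% and 0.117 at f = 10%. Separately, if the historical rate under the chosen definition were 20% rather than 15%, the type I error would be 0.061; at 10% it would be 0.002. The documents give neither f nor these alternative nulls.

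**The case against.** The best defence is that Section 15.4 is the statistical section and gives the fuller rule. It makes restart for viremia, CD4 decline or clinical events a failure, and it cites a definition that requires being off ART. The synopsis objective also speaks of control during a treatment interruption. This defence largely stands.

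It disposes of the reading that a reader might take from the synopsis, namely that participants re-suppressed by restarted drugs would count as controllers and push the endpoint towards 100% without any treatment effect. That could happen only if the synopsis sentence were applied alone. Nor does Section 10.9 promise re-suppression by week 8 of ART: it schedules visits at weeks 4 and 8 and adds more if the viral load is still quantifiable.

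A reader might also count Sections 1.11, 10.9 and 3.1 as rival endpoint definitions. The statement in Section 10.9, "Post-treatment control (defined as viremia <400 copies RNA/mL) should be achieved prior to Week 24 post-virus rebound", sits among the ART-restart criteria, and Section 1.11 adds that ART follows otherwise. It can be met together with Section 15.4. Section 3.1, "To evaluate the impact of this 5-stage regimen on viral load set-point during a treatment interruption", is a one-line objective. These passages use loose labels and do not set competing rules.

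The defence does not remove the conflict over threshold, duration and window, and it does not reach the unclassified restarts. Nor is Section 15.4 itself a single rule: it places the cohort's allowance of two thirds of time points beside its own requirement of 24 weeks below 400, and it leaves a consistent rebound undefined.

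**Conclusion.** The concern holds as a conflict between the synopsis and Section 15.4 over the primary efficacy endpoint, with no rule of precedence. Status can change in both directions, and with a cut-off of 6 in 15 one or two reclassified participants can decide the result (P = 0.019 at 6, 0.077 at 5). It should be corrected before PTC is tabulated.

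The conflict and the status changes follow from the text alone. The antibody-free windows rest on Section 15.4's own week-12 assumption. The error rates for f > 0 and for nulls other than 15% rest on assumed values and show sensitivity only. With every restart counted as failure and a correct 15% null, the exact type I error remains 0.0168.

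**What to change.** - Replace the synopsis definition with the study-specific Section 15.4 rule: off ART throughout, HIV RNA below 400 copies/mL for 24 weeks, by either route. Cite that rule in Section 5.1.
- In Section 15.4, state whether the cohort's two-thirds allowance applies and what makes a rebound consistent.
- In the primary analysis, count any ART restart before the rule is met, for whatever reason, as non-PTC. State how ATI opt-outs are counted, and how participants whose 24 weeks of control are incomplete at week 86 are counted.
- State that the 15% and 5% nulls refer to this definition, or re-derive them.
- Keep HIV RNA below 50 copies/mL off ART as a supportive endpoint.
- Leave the ART-restart criteria in Sections 1.11 and 10.9 as they are. Only reconcile their use of the PTC label with Section 15.4.

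The cost is wording, with no added assessments: Section 15.3 already collects ART resumptions and their triggers. The observed PTC count may be slightly lower.

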| | 
of individuals who achieve PTC will be tabulated and a 2-sided 95% confidence interval obtained by exact calculations for the binomial distribution. The proportion will also be compared to historical controls, with a P-value obtained by likelihood ratio test. For those who initiated ART during acute infection, a literature review indicates that no more than 15% PTC would be expected without intervention. For those who initiated during chronic infection, no more than 5% PTC would be expected. These maximum expected rates will serve as the null hypothesis for our P-value calculations. Evaluation of the acute group will be the primary analysis, while evaluation of the chronic group will be exploratory and provide initial preliminary information on generalizability.
 
Using standard and innovative measures of immunogenicity, we will determine the capacity of our strategies to stimulate broad, functional T cell responses against conserved element HIV epitopes, and comprehensively characterize the impact of the vaccine on several innate and adaptive immune parameters. The size of the active and latent reservoirs before, during and after vaccination will be measured.
 |
| SAMPLE SIZE JUSTIFICATION | 
For the acute group, observing 6 or more PTC among N=15 (40%) will result in $P < 0.05$ versus the null hypothesis of 15%, and the study will have $\geq 80\%$ power if the true chance of PTC with intervention is $\geq 47\%$.
 
For the chronic group, observing even one PTC (20%) would provide some indication of promise, and observing 2 PTC (40%) would produce $P < 0.05$ versus the null hypothesis of 5%.
 |
| PLANNED INTERIM ANALYSES | 
A Safety Monitoring Committee (SMC) will be convened and will meet biannually to review all adverse events and the conduct of the study. Serious adverse events will be monitored by the committee on an ongoing basis throughout the study.
 |

TABLE OF CONTENTS

| | | |
|----------|--|-----------|
| 1 | BACKGROUND | 23 |
| 1.1 | Study background and rationale..... | 23 |
| 1.1.1 | CD8+ T cell immunity in a therapeutic setting | 23 |
| 1.1.2 | Prime-boost vaccine regimen followed by a TLR7 agonists..... | 24 |
| 1.1.3 | TLR7 agonists during ART can induce an SIV cure/remission..... | 24 |
| 1.1.4 | Emerging role of ADCC responses in a therapeutic setting | 25 |
| 1.1.5 | TLR7 agonists and bNAbs induce an SIV cure/remission | 25 |

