Primary efficacy outcome. All subjects will undergo a treatment interruption designed to evaluate the primary outcome of "post-treatment control" (PTC). The proportion of individuals who achieve PTC will be tabulated and a 2-sided 95% confidence interval obtained by exact calculations for the binomial distribution. For those who initiated ART during acute infection, a literature review indicates that no more than 15% PTC would be expected without intervention. For those who initiated during chronic infection, no more than 5% PTC would be expected. These maximum expected rates will serve as the null hypothesis for our P-value calculations. Evaluation of the acute group will be the primary analysis, while evaluation of the chronic group will be exploratory and provide initial preliminary information on generalizability.

Using standard and innovative measures of immunogenicity, we will determine the capacity of our vaccine strategies to stimulate broad, functional T cell responses against novel HIV epitopes, and comprehensively

characterize the impact of the vaccine on several innate and adaptive immune parameters. The size of the active and latent reservoirs before, during and after vaccination will be measured.

Power calculations. For the acute group, observing 6 or more PTC among N=15 (40%) will result in $P < 0.05$ versus the null hypothesis of 15%, and the study will have $\geq 80\%$ power if the true chance of PTC with intervention is $\geq 47\%$.

For the chronic group, observing even one PTC (20%) would provide some indication of promise, and observing 2 PTC (40%) would produce $P < 0.05$ versus the null hypothesis of 5%.

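### The likelihood ratio test for post-treatment control is underspecified; in its usual two-sided chi-square form it gives P<0.05 at 0/15 and can disagree with the planned exact interval

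*Combined protocol and SAP*

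**What the plan says.** The synopsis (Efficacy Evaluations) plans to tabulate the proportion achieving PTC with an exact two-sided 95% binomial confidence interval. It then adds: "The proportion will also be compared to historical controls, with a P-value obtained by likelihood ratio test". For those treated in acute infection, "a literature review indicates that no more than 15% PTC would be expected without intervention"; for the chronic group the corresponding ceiling is 5%. On the use of these ceilings it says: "These maximum expected rates will serve as the null hypothesis for our P-value calculations". The acute group (N=15) is the primary analysis.

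Section 15.6 repeats the exact interval, the two null rates and the power statement, but not the sentence naming the test. Section 15.4 defines PTC and names no test either. The sidedness and reference distribution of the P-value are not given anywhere.

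The decision threshold is stated in the upward direction only: "observing 6 or more PTC among N=15 (40%) will result in" P<0.05 against 15%. Power is given as at least 80% when the true rate is at least 47%. No threshold is given for any other N.

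**The concern.** A likelihood ratio test of a single proportion is most often run by referring the statistic to chi-square on one degree of freedom. That test looks in both directions and is approximate. Here the null rate is a ceiling, so only high counts are evidence against it, and at N=15 the approximation is poor in the lower tail.

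Two things are at stake. First, the primary P-value could fall below 0.05 when nobody controls, a result that fits the ceiling and that the planned exact interval would not call different from 15%. Second, if the number analysed is not 15, the P-value and the interval could point different ways on benefit, with no rule for which prevails.

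**Working it through.** **Inputs.** n=15, null p0=0.15, threshold 6, nominal 0.05, true rate 0.47 (section 15.6). Test: likelihood ratio (synopsis only). The chi-square reference with one degree of freedom is an assumption.

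**Formula.** G = 2[x ln((x/n)/p0) + (n−x) ln((1−x/n)/(1−p0))], with a zero-count term taken as 0.

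**Step 1: reproduce the plan's threshold.**
- 6/15: 12 ln(0.40/0.15) + 18 ln(0.60/0.85) = 11.770 − 6.270 = 5.500, P=0.019.
- 5/15: G=3.126, P=0.077.

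The two-sided chi-square reading therefore gives the stated threshold of 6. The exact binomial test also does (one-sided P=0.017 at 6/15 and 0.062 at 5/15). A one-sided signed-root version at 0.05 does not, since it already rejects at 5/15 (P=0.0385).

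**Step 2: the lower tail.**
- 0/15: G = 30 ln(1/0.85) = 4.876, P=0.027.
- 1/15: P=0.318.

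The rejection region is therefore 0, and 6 or more.

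**Step 3: actual size at p0=0.15.**
- P(X=0) = 0.85^15 = 0.0874.
- P(X≥6) = 0.0168.
- Sum = 0.1042, about twice the nominal 5%.

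**Step 4: the companion interval.** The exact 95% upper limit at 0/15 is 1 − 0.025^(1/15) = 0.218. The interval 0 to 21.8% contains 15%, while the P-value is 0.027.

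**Step 5: fewer than 15 analysed.** The documents give no expected shortfall, so I take N=12 to 14 as an illustrative range.

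| N | Lowest high count with chi-square P<0.05 | Its P | Exact one-sided P | Exact 95% lower limit | P at 0/N | Size |
|---|---|---|---|---|---|---|
| 12 | 5 | 0.026 | 0.024 | 15.2% | 0.048 | 16.6% |
| 13 | 5 | 0.039 | 0.034 | 13.9% | 0.040 | 15.5% |
| 14 | 6 | 0.012 | 0.012 | 17.7% | 0.033 | 11.4% |
| 15 | 6 | 0.019 | 0.017 | 16.3% | 0.027 | 10.4% |

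For 5/13: 10 ln((5/13)/0.15) + 16 ln((8/13)/0.85) = 9.416 − 5.168 = 4.248, P=0.039. The test calls this a difference from 15%; the interval does not. Within this range only N=13 shows the conflict in the benefit direction. The conflict at zero appears at every N shown.

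**Step 6: power of the 6/15 rule.** P(X≥6 | 15, 0.47) = 0.7875, which is 1.25 points below 80%. It reaches 80% at a true rate of 0.476 and is 0.810 at 0.48.

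**Chronic group.** 2/5 against 5% gives chi-square P=0.018 and exact P=0.023, and 0/5 gives P=0.474. The stated P<0.05 holds, and there is no lower-tail problem.

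**The case against.** The plan does not mention chi-square. It asks for exact binomial calculations for the interval immediately before naming the test. If the likelihood ratio statistic is referred to its exact binomial distribution, 0/15 has P=0.104, only 6 or more is rejected, the size is 1.7%, and at N=15 nothing conflicts with the interval. That reading fits the stated threshold equally well. This stands: the 10.4% is conditional on the common software default. The exact reference does not remove the disagreement at 5/13, where its P-value is 0.034, still below 0.05.

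The sentence naming the test may also be a leftover. Section 15.6 repeats the surrounding text without it, and the change log for Version 1.4 records removing the historical-control reference from the power calculation. If so, no test is named at all, which is still a gap for a primary endpoint.

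Two stronger readings are tempting. One is that the plan carries a 10% risk of wrongly claiming efficacy. It does not: success is expressed only as 6 or more, and that has probability 1.7% at a true rate of 15%. Nobody would take zero controllers as benefit, and the opening of section 15 commits to interpreting estimates and intervals rather than P<0.05 alone.

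The other is to count rejection at true rates below 15% (20.8% at 10%, 46.3% at 5%, almost all from 0/15) as type I error. The plan sets the ceiling as the null value. Against a point null of 15%, those rejections are correct, so they are errors only if the null is taken to be every rate up to 15%.

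On power, the shortfall is little more than one point and close to rounding.

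**Conclusion.** The point holds as a specification gap with a definite consequence under the most common reading. With a two-sided chi-square likelihood ratio test, N=15 and p0=0.15, the P-value has size 10.4%, and at 0/15 it contradicts both the ceiling and the planned exact interval. The error that matters for an efficacy claim is 1.7% at N=15, so the stated success rule is sound.

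The choice of test can affect a conclusion on benefit only if the number analysed differs from 15, as at 5/13. That is plausible but not certain. Section 13.3 does not replace those who withdraw after entry, and Appendix C lets participants opt out of the interruption. Section 15.1 makes intention-to-treat primary but does not say how someone who never interrupts ART is counted. If such participants stay in the denominator as non-controllers, N remains 15 in the primary analysis and the issue is confined to the per-protocol analysis or to under-enrolment.

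The power statement is slightly optimistic (78.8% at 47%) and needs only a change of wording. Overall this is worth correcting because it concerns the primary P-value and the correction is nearly free; it does not undermine the design.

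**What to change.** In the synopsis, replace the likelihood ratio test with a one-sided exact binomial test of PTC at or below 15% in the acute group at level 0.025, and name the same test in sections 15.4 and 15.6. For the exploratory chronic group, use the same test against 5%; 2/5 still qualifies (P=0.023).

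This test rejects exactly when the lower limit of the planned exact two-sided 95% interval lies above the null rate. It cannot flag 0/15, keeps 6 or more of 15 (P=0.017), and supplies a rule at other N: 5 of 12, 6 of 13, 6 of 14.

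State in section 15.1 how participants who do not enter the interruption are counted. Restate power as about 79% at a true rate of 47%, or 81% at 48%.

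If the likelihood ratio test is kept, the minimum is to state its sidedness and reference distribution, and which of test and interval governs when they disagree.

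The cost is a few sentences. The threshold at N=15 does not move, and one power figure becomes slightly less favourable.
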